5.1.4.2 Non-Visit Telephone Contacts

Acute Phase Telephone Contacts to Review the DCs up to D29+1 (Cohorts 1, 2, 3 and 4) and D84+8 (Cohorts 2 and 4)

Note: If any of the Acute Phase non-visit contacts fall on a weekend or a holiday, the telephone call may be made on the following business day. All telephone contacts with the participant's parent / guardian / legally authorized representative must be made by a qualified person, such as a physician or qualified study nurse.

^a For CDC COVID testing algorithm, see: https://www.cdc.gov/coronavirus/2019-ncov/lab/resources/Antigen_Testing_Algorithm_2020-12-14_v03_NO_DRAFT_SPW_508.pdf

- 1) Review the information entered in the DC for solicited reactions and unsolicited AEs, AESIs, MAAEs and SAEs. The site staff upon evaluation, if required, will schedule an Illness Visit within the appropriate time window of site notification ([Table 5-4](#)).
- 2) Record relevant information concerning the participant's health status including any changes in medications and immunizations on the telephone contact form, and in the CRF, if required. The site staff, upon evaluation, will schedule an Illness Visit within the stipulated time frame of site notification, if required.
- 3) If an SAE had occurred, follow the instructions in [Section 10](#) for reporting it. Also remind to notify the site in case of an SAE.
- 4) Remind the parent / guardian / legally authorized representative to do the following:
 - Complete the remaining pages of the diary card / electronic diary card and bring them to next visit.
 - Notify the site in case of an SAE.

Day 42+1 Telephone Contact (Cohorts 1, 2, 3 and 4)

- 1) Record relevant information concerning the participant's health status including any changes in medications and immunizations on the telephone contact form, and in the CRF, if required. The site staff, upon evaluation, will schedule an Illness Visit within the stipulated time frame of site notification, if required.
- 2) If an SAE had occurred, follow the instructions in [Section 10](#) for reporting it. Also remind to notify the site in case of an SAE.
- 3) Remind the parent / guardian / legally authorized representative to do the following:
 - Complete the remaining pages of the diary card / electronic diary card and bring them to next visit.
 - Notify the site in case of an SAE.

Telephone Contacts During the RSV Season or Post-vaccination RSV Surveillance

During the RSV season (01 November to 31 March in the northern hemisphere and 01 May to 30 September in the southern hemisphere) or post-vaccination RSV surveillance (at least 5 months after last vaccine administration), make phone contacts every 2 weeks with the parent / guardian / legally authorized representative.

- 1) Record relevant information concerning the participant's health status including any changes in medications and immunizations on the telephone contact form.
- 2) Schedule an Illness Visit within the guidelines and stipulated time frame from the phone contact for a medically attended illness of the following types: fever, URI, LRI or otitis media. If this illness overlaps with the Acute or Post-Acute Phases, the time frames specified for the relevant Acute or Post-Acute phase should be used (see [Table 5-4](#)).

- 3) If a participant had visited any other non-study doctor / hospital for a serious adverse event (SAE) (at any time in the study), schedule a site visit once the participant is discharged to obtain a nasal swab sample for RSV viral detection and [REDACTED] for respiratory pathogens.
- 4) If an SAE had occurred, follow the instructions in [Section 10](#) for reporting it. Remind to notify the site in case of an SAE.

5.1.5 Planned Study Calendar

The following dates are approximate. The actual dates may differ as, for example, the study will not start until all the appropriate regulatory and ethical approvals have been obtained.

Estimated planned study period:

Cohort 1 – 03 September 2020 (FVFP) to 30 April 2021 (LCLS)
Cohort 2 – 11 December 2020 (FVFP) to 31 October 2021 (LCLS)
Cohort 3 – 01 April 2021 (FVFP) to 30 April 2022 (LCLS)
Cohort 4 – 01 June 2021 (FVFP) to 30 April 2023 (LCLS)

Estimated enrollment / 1st vaccination period:

Cohort 1 – 03 September 2020 to 27 October 2020
Cohort 2 – 11 December 2020 to 01 March 2021
Cohort 3 – 01 April 2021 to 31 May 2021
Cohort 4 – From 01 June 2021

Estimated 2nd vaccination period:

Cohort 2 – 05 February 2021 to 26 April 2021
Cohort 4 – From 27 July 2021

Planned date of final clinical study report:

First Interim CSR (6- to 18-month-old participants, Cohorts 1, 2, 3 and at least 90 participants from Cohort 4) – Planned January 2023.

Based on timelines for Cohort 4, assuming 4 months from Day 84 timepoint for the 90th participant (July 2022) to the generation of final key tables for interim data.

Early analysis CSR (all participants) – June 2023

Final CSR – December 2023.

Assuming 4 months from LCLS (April 2023) and 3 months for final statistical analysis and completion of CSR.

5.1.6 Early Safety Data Review

The safety of the investigational product will be continuously monitored by the Sponsor. To allow for a cautious, stepwise approach to vaccine administration, early safety data review (ESDR) will be performed during scheduled SMT meetings:

- Cohort 1
 - D7 post-vaccination ESDR/SMT
 - D28 post-vaccination ESDR/SMT
 - D56 post-vaccination ESDR/SMT

- Cohort 2
 - D7 post-vaccination ESDR/SMT
 - D28 post-vaccination ESDR/SMT
 - D84 post-vaccination ESDR/SMT
- Cohort 3
 - D7 post-vaccination ESDR/SMT
 - D28 post-vaccination ESDR/SMT
 - D56 post-vaccination ESDR/SMT
- Cohort 4
 - D7 post-vaccination ESDR/SMT
 - D28 post-vaccination ESDR/SMT
 - D84 post-vaccination ESDR/SMT

The safety data collected will be entered into the CRBs and summarized by the Sponsor in a blinded manner for each ESDR. The ESDR will be performed by the Sponsor during the SMT meetings. Enrollment will not be paused during SMT reviews.

It is understood that all reviews are based on preliminary data that have not been subjected to validation and database lock. The usual and ongoing process of monitoring safety signals outside of those specified in the protocol-defined early interim safety analysis will continue unchanged.

If at any other time point in the study the predetermined alert threshold for a safety event is reached, regardless of the study time point, the trial will be paused for enrollment in order for an ad-hoc SMT to be convened.

During the safety evaluation, a Bayesian approach based on Posterior Distribution may be used to assess the difference between each RSV formulation and placebo on the following safety endpoints:

- Any Grade 3 lower respiratory tract illness e.g., wheezing, pneumonia, sustained tachypnea, laryngotracheobronchitis (see [Section 9.1.1.3.5](#))
- Grade 3 fever

The probability that the difference of percentages of events between one RSV formulation and Placebo is greater than a pre-specified margin (δ) can be calculated based on posterior distribution, using non-informative prior Beta (1,1) (33) and observed binomial data:

Proba (%RSV - %Placebo > δ)

If this probability is high (e.g., $\geq 80\%$) then it may be recommended to drop the formulation. Thus, it can help decision making for safety evaluation by SMT and/or IDMC (if applicable) and can also be applied at the end of the study.

In cases where the review of data by the SMT does not result in the identification of a potential safety signal, SMT oversight proceeds as assigned in the SMT charter. When a safety signal is identified, the SMT investigates the event(s), completes the Safety Analysis and/or Evaluation Report and decides about the safety signal and further actions and/or recommendations including:

- Extending or pausing the trial and escalate to the Vaccine Adjudication Committee (VAC)
- Investigate and develops a report
- Recommends continuing the trial

Within the investigation, the team may consult with non-clinical safety experts and research team members on whether there is a possible underlying mechanism for the event and review of toxicology data or other internal experts depending on the need.

In case of disagreement in the team, the core team seeks respective functional management advice from the VAC shortly after the SMT meeting. The Vaccine Pharmacovigilance Global Business Unit (PV GBU) Head or Vaccines GBU Clinical & Sciences Head may be also consulted, especially in instance where escalation of the signal for PSB review is in question.

Once the SMT core team agrees that there is a safety signal that can potentially impact the participant's safety, study conduct (pause, extended pause, or termination) or design (modifications needed), the SMT PM informs the Vaccine PV GBU Head who validates the signal and urgently contacts the Vaccines GBU Clinical & Sciences Head and the Chair of the PSB. The decision is made on whether to convene a PSB or not.

Based on the outcomes and recommendations from the PSB, the SMT may carry out any of the following operational actions related to the conduct and oversight of the study including:

- Continue the trial
- Extend the pause to conduct a further evaluation e.g., an ad hoc IDMC
- Modify the trial design, or
- Stop the trial.

An ad-hoc IDMC, which ideally will include at least 2 pediatric respiratory virus vaccine experts, will review upon request of the SMT unblinded study data. The ad-hoc IDMC will upon request review the relevant safety information and available data, including magnitude of vaccine virus shedding. If an ad hoc IDMC meeting is required, the ad hoc IDMC will review the data on safety available at that time point to determine if attributable to an etiology, a cause, or a diagnosis unrelated to the study vaccine, and if the adverse event(s) is associated with shedding of vaccine virus at the time of the event (even if another is identified). If the ad-hoc IDMC decides there is no proven causal relationship between the adverse events and study vaccine, the study can continue unchanged. Based on evaluation of the IDMC, the Sanofi Pasteur SMT will decide if there is a causal relationship between the adverse event and the study vaccine, then SMT will decide whether to:

- Conduct internal signal detection processes (SOP # RDWIN-000390)
- Escalate validated signals to PSB as needed
- Continue the trial
- Modify the trial design (with PSB and ad-hoc IDMC input) or,
- Stop the trial (with PSB and ad-hoc IDMC input).

The following safety parameters will be assessed as part of the early safety review:

- Immediate reactions
- Solicited respiratory and systemic reactions
- Unsolicited reactions i.e., AEs reported as related by the Investigator
- SAEs, MAAEs and AESIs

Enrollment will not be paused during the review. The data will be examined for the following:

- 1) Any deaths, regardless of causality.
- 2) Any vaccine related SAEs.
- 3) Grade 3 fever reported in > 2 participants.
- 4) Any Grade 3 or above solicited adverse events other than fever.
- 5) >1 participant experiencing lower respiratory tract illness of >Grade 2 DAIDS scale (except for wheeze by Brighton Collaboration Severity Scale) during the acute phase (i.e., within 28 days post-vaccination).
- 6) Any participant experiencing an AESI of Grade 3 or above by DAIDS scale (except for wheeze by Brighton Collaboration Severity Scale), including lower respiratory tract illness during the acute phase (i.e., within 28 days post-vaccination).
- 7) >1 participant with a Grade 3 unsolicited AE during the acute phase (i.e., within 28 days post-vaccination).
- 8) Any other pattern of research laboratory values or clinical symptoms other than fever that is considered a significant safety issue by the Investigator.

If any of the above criteria are met, a decision will be made as to whether enrollment in the study will be allowed to resume.

Case unblinding may be performed, if necessary, as determined by the SMT.

5.2 Enrollment and Retention of Study Population

5.2.1 Recruitment Procedures

Before the start of the study the Investigator and/or study staff will determine the recruitment strategy to be used at their site for this study (e.g., advertising, database, direct mailing, word of mouth referrals). Using the relevant methods, they will contact an appropriate pool of potential parents / guardians/ legally authorized representatives and invite them to participate in the study. The sites will ensure that any materials used to recruit participants (e.g., information brochures, letters, pamphlets, posters, other advertisements, etc.) are submitted to Sanofi Pasteur prior to submission to the IRB for approval.

In addition, a parent / guardian / legally authorized representative who brings a child to the study site for routine visit will be invited to enroll the participant in the study, if eligible. Participants may also be recruited from the general population.

5.2.2 Informed Consent Procedures

Informed consent is the process by which a participant's guardian or appropriate legally acceptable representative voluntarily confirms his or her willingness to participate in a particular study. Informed consent must be obtained before any study procedures are performed. The process is documented by means of a written, signed, and dated ICF.

In accordance with GCP, prior to signing and dating the consent form, the participant's guardian/representative must be informed by appropriate study personnel about all aspects of the study that are relevant to making the decision to participate and must have sufficient time and opportunity to ask any questions.

If the participant's guardian /legally authorized representative is not able to read and sign the ICF, then it must be signed and dated by an impartial witness who is independent of the Investigator. A witness who signs and dates the consent form is certifying that the information in this form and any other written information had been accurately explained to and understood by the participant or his / her guardian / representative.

The actual ICF used at each center may differ, depending on local regulations and IEC / IRB requirements. However, all versions must contain the standard information found in the sample ICF provided by the Sponsor. Any change to the content of the ICF must be approved by the Sponsor and the IEC / IRB prior to the form being used.

If new information becomes available that may be relevant to the participant's guardian / legally authorized representative willingness to continue participation in the study, this will be communicated to him / her in a timely manner. Such information will be provided via a revised ICF or an addendum to the original ICF.

Informed consent forms will be provided in duplicate, or a photocopy of the signed consent will be made. The original will be kept by the Investigator, and the copy will be kept by the participant's guardian / legally acceptable representative.

Documentation of the consent process should be recorded in the source documents.

Rationale for Including Participants Unable to Give Consent:

See [Section 1.4](#) for the rationale for conducting this study in pediatric population.

5.2.3 Screening Criteria

There are no screening criteria other than the inclusion and exclusion criteria. The Investigator must review the inclusion and exclusion criteria at enrollment (Visit 01).

5.2.4 Inclusion Criteria

An individual must fulfill *all* of the following criteria to be eligible for study enrollment (Visit 01):

- 1) Aged 6 through 18 months at D0.^a
- 2) Informed consent form has been signed and dated by the parent(s) / guardian / or other legally authorized representative (and by independent witness if required by local regulations).
- 3) Participant and parent / guardian / legally authorized representative are able to attend all scheduled visits and to comply with all trial procedures.

5.2.5 Exclusion Criteria

An individual fulfilling *any* of the following criteria is to be excluded from trial enrollment:

- 1) Participation at the time of study enrollment (or in the 6 weeks preceding the first trial vaccination) or planned participation during the present trial period in another clinical trial investigating a vaccine, drug, medical device, or medical procedure.
- 2) Receipt of any of the following vaccines prior to enrollment:
 - any influenza vaccine within 7 days prior, or
 - any inactivated vaccine within the 14 days prior, or
 - live-attenuated rotavirus vaccine within the 14 days prior, or
 - any live vaccine, other than rotavirus vaccine, within the 28 days prior, or
 - another investigational vaccine or investigational drug within 28 days prior.
- 3) Previous receipt of a licensed or investigational RSV vaccine or previous receipt or planned administration of any anti-RSV product (such as ribavirin or RSV immune globulin [IG] or RSV monoclonal antibody).
- 4) Receipt of immune globulins, blood or blood-derived products in the past 6 months prior to enrollment.
- 5) Known or suspected congenital or acquired immunodeficiency; or receipt of immunosuppressive therapy, such as anti-cancer chemotherapy or radiation therapy, within the preceding 6 months; or long-term systemic corticosteroid therapy (prednisone or equivalent for more than 2 consecutive weeks within the past 3 months).
- 6) Probable or confirmed case of Coronavirus Disease 2019 (COVID-19).
- 7) Known systemic hypersensitivity to any of the vaccine components, or history of a life-threatening reaction to the vaccine used in the trial or to a vaccine containing any of the same substances.^b

^a 6 through 18 months means from 6th month after birth to the day before the 19th month after birth.

^b The components of the study vaccine are listed in Section 6.1 and in the Investigator's Brochure.

- 8) Any chronic illness.
 - Chronic illness may include, but is not limited to, cardiac disorders, lung disease (including any history of reactive airway disease, receipt of bronchodilator therapy, or medically diagnosed wheezing), renal disorders, auto-immune disorders, diabetes, psychomotor diseases, and known congenital or genetic diseases
- 9) Any history of medically diagnosed wheezing.
- 10) Any acute febrile, respiratory or gastrointestinal illness in the past 24 hours that according to investigator judgment is significant enough to interfere with successful inoculation on the day of vaccination. A prospective participant should not be included in the study until the condition has resolved or the febrile event has subsided.
- 11) Receipt of any of the following medications within 3 days prior to study enrollment:
 - systemic antibacterial, antiviral, antifungal, anti-parasitic, or antituberculous agents, whether for treatment or prophylaxis, or
 - intranasal medications, or
 - other prescription medication except as permitted concomitant medications (prescription or non-prescription) including nutritional supplements, medications for gastroesophageal reflux, eye drops, and topical medications, including (but not limited to) cutaneous (topical) steroids, topical antibiotics, and topical antifungal agents.
- 12) Receipt of salicylate (aspirin) or salicylate-containing products within the 28 days prior to enrollment.
- 13) Deprived of freedom in an emergency setting or hospitalized involuntarily.
- 14) Identified as a natural or adopted child of the Investigator or employee with direct involvement in the proposed study.
- 15) Any previous anaphylactic reaction.
- 16) Any previous vaccine-associated adverse reaction that was Grade 3 or above. Note: if grading is not possible, determine if the reaction was considered severe or life-threatening; if so, it is exclusionary.
- 17) Member of a household that contains, or will contain, an infant who is less than 6 months of age at the enrollment date (or in the 6 weeks preceding the first trial vaccination) through Day 28.
- 18) Member of a household that contains another child/other children who is/are, or is/are scheduled to be, enrolled in this study in the same year AND the date of enrollment will not be concurrent with the other participant(s) living in the household (i.e., all eligible children from the same household must be enrolled on the same date).
- 19) Member of a household that contains an immunocompromised individual, including, but not limited to:
 - a person who is HIV infected
 - a person who has received chemotherapy within the 12 months prior to enrollment
 - a person receiving immunosuppressant agents
 - a person living with a solid organ or bone marrow transplant.

- 20) Attends a daycare facility and shares a daycare room with infants less than 6 months of age, and parent/ guardian / legally authorized representative is unable or unwilling to suspend daycare for 28 days following inoculation.
- 21) Scheduled administration of the following after planned inoculation:
 - any influenza vaccine within 7 days after, or
 - inactivated vaccine or live-attenuated rotavirus vaccine within the 14 days after, or
 - any live vaccine other than rotavirus in the 28 days after, or
 - another investigational vaccine or investigational drug in the 56 days after.
- 22) Born at less than 34 weeks gestation.
- 23) Born at less than 37 weeks gestation and less than 1 year of age at the time of enrollment.
- 24) Current suspected or documented developmental disorder, delay, or other developmental problem.
- 25) Any previous receipt of supplemental oxygen therapy in a home or hospital setting, except the temporary receipt of supplemental oxygen for transient tachypnea in newborn.

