5.1.4.1 In-Person Visits

Visit 01 (Day 0) for Cohorts 1, 2, 3 and 4

Timelines for the end of enrollment (Visit 01), vaccination and RSV surveillance per hemisphere are shown in [Table 5-3](#).

Table 5-3: Timelines for end of enrollment and vaccination per hemisphere

	Infants and Toddlers 6 to 18 Months of Age			
	Northern Hemisphere (USA) Cohort 1 (1 administration)	Southern Hemisphere (Latin America) Cohort 2 (2 administrations)	Northern Hemisphere (USA) Cohort 3 (1 administration)	Northern and Southern Hemispheres (USA and Latin America) Cohort 4 (2 administrations)
Earliest day for enrollment (Visit 01)	01 August 2020	01 November 2020	01 April 2021	USA - 01 June 2021 Canada – May 2022 Chile - November 2021 Honduras - April 2022 South Africa - June 2022
Last day for enrollment (Visit 01)	5 days before the start of the RSV season	61 days before the start of the RSV season	31 May 2021	Not applicable
Last day for Visit 03 (D56) Vaccination 2	-	5 days before the start of the RSV season	-	Not applicable

Visit 01 (Day 0): Enrollment, Randomization, and Vaccination Procedures for Cohorts 1, 2, 3 and 4 (All Participants)

- 1) Give the participant's parent / guardian / legally authorized representative information about the study, obtain written informed consent, and give him / her a signed copy.
- 2) Collect demographic data (including date of birth, sex, race, and ethnicity).
- 3) Check inclusion and exclusion criteria for eligibility.
- 4) Obtain verbal medical history about the participant, including past and ongoing medication, any signs and symptoms, and developmental delays.
- 5) Review any past medical records including the immunization record to ensure participant will not meet exclusion criteria 2, 3 and 21.
- 6) Prior to randomization conduct a full physical examination including body temperature, heart rate, respiratory rate, weight, length and assessment of HEENT [head, ears, eyes, nose, and throat], lungs, heart, and abdomen, musculoskeletal, age-appropriate neurological and skin exam.
- 7) Perform Coronavirus Disease 2019 (COVID-19) point of care diagnostic test (POC).
- 8) Contact the IRT for participant number, randomization and dose number based on age subgroup. Additional information regarding randomization is in the Operating Guidelines.

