5.2.7 Contraindications for Subsequent Vaccinations

5.2.7.1 Temporary Contraindications

Should a participant experience one of the conditions listed below at Day 0 (Cohorts 1, 2, 3 and 4) or Day 56 (Cohorts 2 and 4), the Investigator will postpone further vaccination until the condition is resolved. Postponement must still be within the timeframe for vaccination i.e., within 5 days of randomization for Day 0 (Cohorts 1, 2, 3 and 4) and within 7 days of Day 56 (Cohorts 2 and 4).

- 1) Any acute febrile illness (rectal temperature $\geq 38.0^{\circ}\text{C}$ [$\geq 100.4^{\circ}\text{F}$]), acute otitis media, upper and lower respiratory signs or symptoms (including but not limited to rhinorrhea, cough, and pharyngitis), or nasal congestion in the past 24 hours that according to investigator's judgment is significant enough to interfere with successful absorption of the study product.
- 2) Receipt of any of the following before any study vaccination or scheduled administration after any study vaccination:
 - any influenza vaccine within 7 days prior, or
 - any inactivated vaccine or live-attenuated rotavirus vaccine within the 14 days prior, or
 - any live vaccine, other than rotavirus vaccine, within the 28 days prior, or
 - another investigational vaccine or investigational drug within 28 days prior.

All eligible participants from the same household who are enrolled on the same date must receive the study product on the same date, and therefore if one child experiences illness as above, product administration should be deferred for both children.

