9.1 Primary Endpoints and Assessment Methods

9.1.1 Safety

9.1.1.1 Safety Definitions

The following definitions are taken from the ICH E2A Guideline for Clinical Safety Data Management: Definitions and Standards for Expedited Reporting.

Adverse Event (AE):

An AE is any untoward medical occurrence in a patient or in a clinical investigation participant administered a medicinal product and which does not necessarily have a causal relationship with this treatment. An AE can therefore be any unfavorable and unintended sign (including an abnormal laboratory finding, for example), symptom or disease temporally associated with the use of a medicinal product, whether or not considered related to the medicinal product.

Therefore, an AE may be:

- A new illness
- The worsening of a pre-existing condition
- An effect of the vaccination, including the comparator
- A combination of the above

All AEs include serious and non-serious AEs.

Surgical procedures are not AEs; they are the actions taken to treat a medical condition. It is the condition leading to the action taken that is the AE (if it occurs during the study period).

Pre-existing medical conditions are not to be reported as AEs. However, if a pre-existing medical condition worsens following study interventions in frequency or intensity, or if according to the Investigator there is a change in its clinical significance, this change should be reported as an AE (exacerbation). This applies equally to recurring episodes of pre-existing conditions (e.g., asthma) if the frequency or intensity increases post-vaccination.

Serious Adverse Event (SAE):

Serious and *severe* are not synonymous. The term *severe* is often used to describe the intensity of a specific event as corresponding to Grade 3. This is not the same as *serious*, which is based on participant / event outcome or action criteria usually associated with events that pose a threat to a participant's life or functioning. Seriousness, not severity, serves as a guide for defining regulatory reporting obligations.

An SAE is any untoward medical occurrence that at any dose

- Results in death
- Is life-threatening^a
- Requires inpatient hospitalization or prolongation of existing hospitalization^b
- Results in persistent or significant disability / incapacity^c
- Is a congenital anomaly / birth defect
- Is an important medical event (IME)

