Intensity scale*	Grade 1: $\geq 38.0^{\circ}\text{C}$ to $\leq 38.5^{\circ}\text{C}$ or $\geq 100.4^{\circ}\text{F}$ to $\leq 101.3^{\circ}\text{F}$ Grade 2: $> 38.5^{\circ}\text{C}$ to $\leq 39.5^{\circ}\text{C}$ or $> 101.3^{\circ}\text{F}$ to $\leq 103.1^{\circ}\text{F}$ Grade 3: $> 39.5^{\circ}\text{C}$ or $> 103.1^{\circ}\text{F}$	Grade 1: 1 episode per 24 hours Grade 2: 2–5 episodes per 24 hours Grade 3: ≥ 6 episodes per 24 hours or requiring parenteral hydration	Grade 1: < 1 hour Grade 2: 1–3 hours Grade 3: > 3 hours	Grade 1: Sleepier than usual or less interested in surroundings Grade 2: Not interested in surroundings or did not wake up for a feed / meal Grade 3: Sleeping most of the time or difficult to wake up	Grade 1: Eating less than normal Grade 2: Missed 1 or 2 feeds / meals completely Grade 3: Refuses ≥ 3 feeds / meals or refuses most feeds / meals	Grade 1: Easily consolable Grade 2: Requiring increased attention Grade 3: Inconsolable

* For all reactions but fever, the parent / guardian / legally authorized representative will record the intensity level (Grade 1, 2, or 3) in the diary card. For fever, they will record the body temperature, and the classification as Grade 1, 2, or 3 will be assigned based on the information in the diary card.

Important notes for the accurate assessment of temperature:

Parents / guardians / legally authorized representatives are to measure body temperature once per day, preferably always at the same time. The optimal time for measurement is the evening, when body temperature is the highest. Temperature is also to be measured at the time of any apparent fever. The observed daily temperature and the route of measurement are to be recorded in the diary card, and the highest temperature will be recorded by the site in the CRB. The preferred route for this study is rectal. Pre-vaccination temperature is also systematically collected by the investigator on the source document. Tympanic thermometers must not be used.

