4.4.1.1.4 Time of Onset

Time of onset is derived from the daily intensities computed as described in Section 4.4.1.1.1. It corresponds to the first day with intensity of Grade ≥ 1 .

Note: If a reaction is not continuous (i.e., reaction occurs over two separate periods of time intervened by at least one daily intensity Missing or None) then the time of onset is the first day of the first occurrence.

Time of onset period is displayed as D0-D3, D4-D7, D8-D14, D15-D28.

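### Nasal symptoms that began before a dose can be counted as related administration-site reactions, because the SAP derives solicited presence and onset without using pre-dose nasal status

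*Protocol*

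**What the plan says.** **Who may be dosed.** Exclusion criterion 10 (Protocol 5.2.5) covers acute illness, whether with fever or of the airways or gut, if it was present "in the past 24 hours that according to investigator judgment is significant enough to interfere with successful inoculation on the day of vaccination". Temporary contraindication 1 (Protocol 5.2.7.1), which applies at D0 and D56, names rhinorrhea and nasal congestion, but again only when judged "significant enough to interfere with successful absorption of the study product".

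**What is looked at before dosing.** Visit 01 (Protocol 5.1.4.1) has staff "Obtain verbal medical history about the participant, including past and ongoing medication, any signs and symptoms, and developmental delays" and perform a full examination, including the nose, before randomization. Visit 03 for Cohorts 2 and 4 includes an ear, eye, nose and throat examination before the second dose.

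**What reaches the CRB.** Under Protocol 5.2.6, conditions present before enrollment go into the source document. The CRB takes significant diagnoses, discourages symptoms in place of a diagnosis, and holds no dates or coding. Temperature is named explicitly: "Pre-vaccination temperature is also systematically collected by the investigator on the source document". The Tables of Study Procedures also send vital signs to the eCRF. Nasal findings have no such provision.

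**How a nasal reaction is defined and derived.** Table 9-1 requires at least two days in a row for both nasal terms, and a symptom needing no medical intervention is Grade 1. SAP 4.4.1.1.3 scores any Grade 1 to 5 in the period as presence. For onset, SAP 4.4.1.1.4 states "It corresponds to the first day with intensity of Grade" 1 or higher. Solicited reactions are related by convention (Protocol 9.1.1.1 and 9.1.1.3.6; SAP 5.3.1.2).

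**What is said about earlier onset.** Protocol 9.1.1.1 states "Pre-existing medical conditions are not to be reported as AEs", with worsening as the exception, and describes solicited reactions in terms of onset after vaccination. SAP 4.4.1.2.4 removes events with onset before vaccination, but only for unsolicited AEs.

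**The concern.** Rhinorrhea and nasal congestion are the only two solicited administration-site reactions. They belong to a primary safety endpoint of a live intranasal vaccine and feed a descriptive choice of dose. The protocol's principle is that a condition already present is not an event unless it worsens. The SAP applies a version of this to unsolicited AEs and is silent for solicited reactions.

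A cold that starts the day before dosing and runs on for several days fits the SAP's rule for a reaction with onset on D0, and no causality judgement is made afterwards. Cohort 4 is dosed at any time of year, including winter, so such children are to be expected. Two things are at stake. The rates in each arm, and the contrast with placebo, would mix background illness with new reactions. The onset distribution would be pulled toward the first days, whereas Protocol 5.1.2 places maximal vaccine-virus replication typically no earlier than Day 7.

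**Working it through.** **The plan's own figure.** The plan gives no figure for this point. Its only precision statement (Protocol 12.5, SAP 5.5) reproduces: 1 − 0.97^100 = 0.952 and 1 − 0.9625^80 = 0.953, both stated as 95%. The point does not depend on it.

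**Inputs.** From the documents: 100 low-dose, 80 high-dose and 120 placebo participants, with 60 per arm in Cohort 4. Assumed, because the documents give none of these:
- b, the share whose pre-dose nasal symptom is counted: 5% to 25%, equal across arms
- new-onset rates r: 50% on RSV and 35% on placebo, a 15-point difference
- for timing: a 40% new-onset rate, of which 15% truly starts on D0-D3

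**Rates and difference under the current rule.** Observed rate = b + (1 − b)r. The b terms cancel in the contrast, so observed difference = (1 − b)(r_RSV − r_placebo).

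| b | RSV | Placebo | Difference |
|---|---|---|---|
| 0 | 50.0% | 35.0% | 15.00 points |
| 5% | 0.05 + 0.95×0.50 = 52.5% | 0.05 + 0.95×0.35 = 38.25% | 14.25 points |
| 10% | 55.0% | 41.5% | 13.50 points |
| 25% | 0.25 + 0.75×0.50 = 62.5% | 0.25 + 0.75×0.35 = 51.25% | 11.25 points |

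The two-day definition lowers b. If 20% of children have a symptom at dosing and half of these are counted, b is 10% and the difference is 13.5 points.

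**Against sampling error.** The approximate 95% half-width for 100 vs 120 is 1.96 × √(0.50×0.50/100 + 0.35×0.65/120) = 13.0 points. For 60 vs 60 it is 1.96 × √(0.50×0.50/60 + 0.35×0.65/60) = 17.5 points. The loss of 0.75 to 3.75 points is well inside both.

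**Onset.** Reported D0-D3 share = [b + (1 − b)×0.40×0.15] / [b + (1 − b)×0.40]. At b = 5% this is 0.107/0.430 = 25%. At b = 25% it is 0.295/0.550 = 54%. The assumed true share is 15%, so onset is affected more than the difference.

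**Candidate remedies.**
- *Count only if absent or worsened, same denominator.* Ignoring the few who worsen, the rate is (1 − b)r. At b = 5%: 47.5% vs 33.25%, a difference of 14.25 points. At b = 25%: 37.5% vs 26.25%, a difference of 11.25 points. The shrinkage is unchanged and the rates are now too low.
- *Restrict numerator and denominator to participants without the symptom before that dose.* The rate is r: 50% vs 35%, a difference of 15 points. The bias is removed under the model.

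**The case against.** The strongest reply is that the plan already limits the problem. Much of it stands:

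- A reader might infer that nasal status before dosing is not recorded at all. The documents do not support that: symptoms are asked about at Visit 01, the nose is examined before both doses, and pre-enrollment conditions go to source. The gap is in the CRB requirement and the SAP derivation. The CRB itself, its completion instructions and the Operating Guidelines are not among the documents, so a nasal item may exist there.
- A reader might infer that every pre-dose symptom is counted. The two-day definition removes brief ones. Nasal grades are assigned when the diary card is reviewed, and the general rule on pre-existing conditions could lead a site to leave out an unchanged symptom. But nothing instructs sites to do so for diary items, so handling may vary. The SAP is better described as silent than as contradicting the protocol.
- A reader might infer that an excess around D7 would be hidden. It would not: SAP 4.4.1.1.3 tabulates presence separately for D4-D7 and later periods, by group. Only first onset is pulled forward.
- Placebo is included in every cohort to show background illness, and the relatedness convention is deliberate and conservative. Placebo reveals the inflation, but subtracting it does not undo the (1 − b) factor.
- All analyses are descriptive and every magnitude input is assumed. That argues for a modest remedy.

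**Conclusion.** The point holds in a limited form. The SAP has no baseline rule for solicited nasal reactions, so a symptom that began before the dose and lasts can be reported as a related reaction with D0 onset. The effect is higher rates in all arms, an absolute difference reduced by the factor (1 − b), and first onsets moved toward D0-D3. For an assumed b of 5% to 25%, a 15-point difference loses 0.75 to 3.75 points, which is small against half-widths of about 13 to 17.5 points. No size can be taken from the documents.

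The factor rests on b being equal across arms. Randomization supports this on average within a cohort at dose 1. It is less secure at dose 2, where pre-dose status arises after randomization, and in the pooled-cohort tables of SAP 5.1, because Cohort 4 supplies 60 of 80 high-dose, 60 of 100 low-dose and 60 of 120 placebo participants. The documents do not show that the vaccine's nasal profile would be misjudged. This is a cheap improvement, not a flaw that undermines the safety analysis.

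**What to change.** 1. From the examinations already done at Visit 01 and Visit 03, enter presence and grade of rhinorrhea and nasal congestion before dosing in the CRB. If the CRB can no longer change, abstract them from source documents.
2. Report the number with each pre-dose symptom by vaccine group and dose.
3. Keep the current count as the main analysis. Add a supplementary analysis of presence and onset restricted to, or stratified by, participants without that symptom before that dose, with the denominator restricted as well.
4. In participants with a pre-dose symptom, report worsening in grade.
5. Do not make absent-or-worsened with an unchanged denominator the main rule: it keeps the same shrinkage, understates rates, and is less conservative for a live vaccine.

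If pre-dose status cannot be recovered, showing nasal reactions with and without those starting on D0, beside placebo, is a partial substitute.

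The cost is two CRB items per dose, one extra table, a slightly smaller n in the supplementary analysis, and a caveat that pre-dose status at dose 2 is post-randomization. No dosing or eligibility rule changes.
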